13.3.4.1 Clinical Tolerance Endpoints

Peak nasal inspiratory flow, defined as the change in PNIF relative to the pre-allergen exposure PNIF measurement during the NAC (Delta PNIF AUC_{0-1hr}), will be analyzed using a longitudinal repeated measures model on data from years 1, 2, and 3 with a covariate for baseline Delta PNIF AUC_{0-1hr}.

The size of the early intradermal test response will be analyzed using a longitudinal repeated measures model on data from years 1, 2, and 3 with a covariate for the size of the early intradermal test response at baseline. A similar model will be used to analyze the late intradermal test response.

The size of the skin prick test endpoint titration response will be analyzed using a longitudinal repeated measures model on data from years 1, 2, and 3 with a covariate for the size of the skin prick test endpoint titration response at Visit 0.

Weekly seasonal symptoms (VAS 0-10 cm), CSMS and miniRQLQ will be summarized separately using the trapezoidal rule to estimate the VAS AUC, CSMS AUC, and miniRQLQ AUC at baseline, year 1, 2, and 3 respectively. The AUC of pollen counts collected weekly during the pollen season in year 1, 2, and 3 will be estimated similarly. A longitudinal repeated measures model will be applied to VAS AUC, CSMS AUC, and miniRQLQ AUC from years 1, 2, and 3 with a time-varying covariate for the AUC of pollen count and a covariate for baseline VAS AUC, baseline CSMS AUC, or baseline miniRQLQ AUC respectively.

MRSUI will be analyzed using a longitudinal repeated measures model on data measured twice (in-season in June/July and out-of-season in November/December) in years 1, 2, and 3 with a time-varying covariate for baseline in-season and out-of-season MRSUI.

Global Evaluation No. 1 will be analyzed using a longitudinal repeated measures model on data from years 1, 2, and 3 with a covariate for baseline Global Evaluation No. 1.

Global Evaluation No. 2 will be analyzed using a longitudinal repeated measures model on data from years 1, 2, and 3 without any additional covariates.

Using each of the above models, Secondary Objective 1 will be addressed by applying a contrast in least squares means at year 3 between the combination of SLIT and dupilumab arm and double-placebo arm.

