Secondary Endpoint(s)	
Clinical tolerance endpoints at year 3, one year after completion of study treatment. The comparison will be between the combination of SLIT and dupilumab and the double-placebo arms.
 
 1. Peak nasal inspiratory flow (Delta PNIF AUC_{0-1hr}) 2. Peak NAC TNSS (0-1hr) 3. Size of early and late intradermal skin test response 4. Size of the skin prick test endpoint titration response 5. Seasonal outcomes 
 1. Weekly seasonal symptoms (Visual Analogue Scale [VAS] 0-10 cms) and combined symptom medication scores (CSMS) 2. Weekly rhinitis quality of life scores (Juniper mini-Rhinoconjunctivitis Quality of Life Questionnaire [miniRQLQ]) measured in-season 3. Modified Rhinitis Symptom Utility Index (MRSUI) measured in-season and out-of-season 4. Global Evaluations No. 1 and No. 2 after the season 
Clinical desensitization endpoints at year 1 and 2 whilst on study treatment. The comparison will be between the combination of SLIT and dupilumab and the double-placebo arms.
 
 6. TNSS AUC_{0-1hr} 7. Delta PNIF AUC_{0-1hr} 8. Size of early and late intradermal skin test response 9. Size of skin prick test endpoint titration response

	
10. Seasonal outcomes
 
 1. Weekly seasonal symptoms (VAS 0-10 cms) and CSMS 2. Weekly rhinitis quality of life scores miniRQLQ measured in-season 3. MRSUI measured in-season and out-of-season 4. Global Evaluations No. 1 and No. 2 after the season 
Safety Endpoints
 
The number, severity, and relatedness of local and systemic AEs and SAEs reported during screening, at baseline, during years 1 and 2 whilst on study treatment, and during year 3 (one year after completion of study treatment). Each treatment arm will be summarized separately.

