b) Peak nasal inspiratory flow (Delta PNIF AUC _{0-1hr}) at year 3 c) Peak TNSS at year 3 d) NAC TNSS AUC _{0-1hr} at year 2 e) NAC TNSS AUC _{0-1hr} at year 2, for treatment effect of SLIT/dupilumab arm versus	a) Size of early intradermal skin test response at year 3 b) Size of late intradermal skin test response at year 3 c) Skin prick test endpoint titration response, as defined by the Provocative Concentration at 5mm (PC5) at year 3	a) Weekly seasonal combined symptom medication scores (CSMS) at year 3 using “in-season” data b) Weekly rhinitis quality of life scores (miniRQLQ) measured in-season at year 3 using “in-season” data

SLIT plus dupilumab placebo arm		c) MRSUI measured in-season at year 3 d) Global Evaluation No. 1 at year 3 e) Global Evaluation No. 2 at year 3
---------------------------------	--	---

*Note: For all key secondary endpoints, unless otherwise stated, the treatment effect being tested is SLIT/dupilumab arm *versus* double-placebo arm.

The following biological arguments support each sub-family being independent enough such that each sub-family will be tested at their own alpha of 0.05:

- The primary and key secondary endpoints within the clinically-implicated sub-family refer to responses after a grass pollen allergen challenge in the target organ. This target organ (i.e. the nose) shares a common lymphatic drainage to the sublingual mucosa, the site of application of grass pollen sublingual tablets.
- The biomarker sub-family refers to responses after a grass pollen allergen challenge in the skin that is remote from the nose and its lymphatic drainage and therefore is likely to have a distinct underlying mechanism.
- The survey questionnaire sub-family refers to participant-recorded outcomes of the severity of their hay fever during natural seasonal exposure to grass pollen, rather than a controlled experimental allergen challenge in either the nose or skin.
- For these reasons the 3 sub-families of endpoints may be regarded as distinct for the statistical analyses.

Secondary and exploratory endpoints detailed in this SAP which are not primary nor key-secondary, as well as time points and pairwise comparisons other than those listed above, may have p-values reported for descriptive purposes only, as a means for hypothesis generation.

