9.2.8. Seasonal outcome 3: MRSUI measured in-season and out-of-season

The Modified Rhinitis Symptom Utility Index (MRSUI) questionnaire will be collected twice prior to treatment (at Visit -2 in-season and at Visit 0 out-of-season) and twice (in-season in June/July and out-of-season in November/December) in years 1, 2, and 3. At each visit, the total MRSUI score will be calculated as the sum of the numeric responses to all 10 questions. Higher scores indicate a worse outcome, where the maximum score per visit is 25.

The total MRSUI score will be analyzed using a longitudinal repeated measures model in two ways:

1. Main model for key secondary endpoint and multiplicity control: Modeling only in-season assessments (year 1, year 2, and year 3) with a covariate for baseline in-season total MRSUI score (from Visit -2).
2. Exploratory model: Modeling the in-season assessments minus the prior out-of-season assessment at each year. The time-varying impact of the out-of-season assessments will be accounted for by handling each prior out-of-season assessment as a new baseline value at each year. For example, the first in-season assessment at year 1 will subtract the baseline out-of-season total MRSUI score (from Visit 0).

9.2.9. Seasonal outcome 4: Global Evaluations No. 1 and No. 2 after the season

The Global Evaluation No. 1 questionnaire will be collected after the grass pollen season, annually in years 1, 2, and 3. At each visit, the total Global Evaluation No. 1 score will be calculated as the sum of the numeric responses (0-3) to all 6 questions. Higher scores indicate a worse outcome/severity, where the maximum score per visit is 18.

If 1 or 2 questions were not answered at a particular visit (including baseline), then the total Global Evaluation No. 1 score will be imputed using the following method. If 3 or more questions are missing then the total sum will be left missing.

- Calculate the average of the non-missing question numeric responses for the same participant/visit at which the missing question(s) exist
- Impute the numeric response for the missing question(s) with that average
- Calculate the total sum including the imputed numeric responses for the missing questions

The total Global Evaluation No. 1 score will be analyzed using a longitudinal repeated measures model on data from years 1, 2, and 3 with a covariate for baseline total Global Evaluation No. 1 score.

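### No SAP model takes out-of-season MRSUI as its outcome, and the year-3 out-of-season score enters no model, although both documents list MRSUI in both seasons as a secondary endpoint

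*SAP*

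**What the plan says.** Protocol 3.3 and SAP Section 3 both carry the year-3 item "Modified Rhinitis Symptom Utility Index (MRSUI) measured in-season and out-of-season", for the combination versus double-placebo comparison. Both repeat it in shorter form for years 1 and 2.

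Protocol 13.3.4.1 plans a repeated-measures model "on data measured twice (in-season in June/July and out-of-season in November/December) in years 1, 2, and 3", with in-season and out-of-season baselines as a time-varying covariate. It takes the arm contrast at year 3, and 13.3.4.2 adds contrasts at years 1 and 2.

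SAP 9.2.8 keeps both seasons in its heading and then states: "The total MRSUI score will be analyzed using a longitudinal repeated measures model in two ways".

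- Main model, which carries the key secondary: "Modeling only in-season assessments (year 1, year 2, and year 3) with a covariate for baseline in-season total MRSUI score", the baseline being Visit -2.
- Exploratory model: "Modeling the in-season assessments minus the prior out-of-season assessment at each year". The worked example takes the Visit 0 score away from the year-1 in-season score.

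Table 2 in SAP 8.5 places only "MRSUI measured in-season at year 3" under multiplicity control. SAP Section 13 lists five changes from the protocol, and none concerns MRSUI.

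**The concern.** A listed secondary endpoint covers two seasons. The protocol puts both seasons on the outcome side of the model, and the SAP leaves one of them there. Followed as written, SAP 9.2.8 yields no arm comparison of out-of-season MRSUI in any year. A reader who checks Section 13 would conclude that the protocol analysis of MRSUI still stands.

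The out-of-season score also helps to interpret the in-season one. MRSUI is self-reported, and Protocol 1.2.1 gives local mouth reactions in 46-61% of people on active SLIT, so some participants may guess their arm. A similar arm difference outside the grass season would caution against reading the in-season difference as grass-specific.

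**Working it through.** **Score range.** Protocol Appendix 13 has five frequency items scored 0-3 and five bother items scored 0-2. The maximum is 5 × 3 + 5 × 2 = 25, as SAP 9.2.8 states.

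**Which assessments enter which model.** Visits come from Protocol Appendices 1, 2 and 5. Appendix 5 collects MRSUI only at S3, S5, S8, S10, S13 and S15, so the preceding out-of-season score is unambiguous.

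| Assessment | Period | Main model | Exploratory model |
|---|---|---|---|
| Visit -2 | baseline, in-season | covariate | not used |
| Visit 0 | baseline, out-of-season | not used | subtracted from S3 |
| S3 | year 1, in-season | outcome | S3 − Visit 0 |
| S5 | year 1, out-of-season | not used | subtracted from S8 |
| S8 | year 2, in-season | outcome | S8 − S5 |
| S10 | year 2, out-of-season | not used | subtracted from S13 |
| S13 | year 3, in-season | outcome | S13 − S10 |
| S15 | year 3, out-of-season | not used | not used |

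Seven of the eight are used somewhere and one, S15, is not. S15 follows the last in-season visit, so it can never be a preceding value.

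**Whether other text fills the gap.** SAP 9.2 applies the primary model methodology to secondary endpoints unless a subsection says otherwise, and 9.2.8 does. The pairwise differences promised in 9.2 are those the models estimate, and none estimates this one. SAP 9.3 reuses the same models for the other comparisons. Leaving out-of-season MRSUI out of Table 2 removes alpha control but does not remove the endpoint.

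**What the exploratory model can show.** Write D_in(k) and D_out(k) for the combination minus double-placebo difference at year k. The exploratory contrast at year k estimates D_in(k) − D_out(k−1).

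- Year 1: Visit 0 precedes treatment, so D_out(0) is expected to be 0 under randomisation. The contrast is in expectation just D_in(1), and a shift common to both seasons is not removed.
- Years 2 and 3: the contrasts are D_in(2) − D_out(1) and D_in(3) − D_out(2). A shift present in both terms cancels.
- D_out(3) appears in neither model.

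**Why year 3 differs from year 2.** Using the earliest dates in the visit windows of Protocol 8.5, in days after Visit -1:

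- Visit 0 is at 28 or later, so week 104 falls at 28 + 728 = 756 or later.
- S10 is at about 730 − 14 + 28 = 744 or later, close to the end of dosing.
- S15 is at about 1095 − 14 + 28 = 1109 or later. From 756, that is 353 days, or about a year.

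S15 is therefore the out-of-season score taken about a year off treatment, which is the tolerance time point that the endpoint names.

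**Number of scores.** Protocol 13.6 expects 30 per arm with a year-3 challenge. If the same people attend S15, that is 3 × 30 = 90 unused scores, of which 2 × 30 = 60 bear on the named contrast.

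**The case against.** The strongest reply is that the protocol is less specific than it looks. Both documents list MRSUI as one item. Protocol 13.3.4.1 describes one model with a year-3 contrast and names no season term, no treatment-by-season interaction and no season-specific contrast. Read literally, it could mean a single contrast pooled over both seasons. A reader might infer that a separate out-of-season estimate was promised and withdrawn. The text does not establish that. What stands is narrower: out-of-season scores were outcome data in the protocol and are not in the SAP, and this is undeclared.

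A reader might also infer that the SAP ignores the out-of-season score altogether. It does not: Visit 0, S5 and S10 are used as subtracted terms.

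Nor does the omission leave the in-season result without any check on grass specificity. At years 2 and 3 the exploratory model removes a shift common to both seasons, although year 3 is paired with a score from about the end of dosing.

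The value of the missing contrast is also uncertain. Neither document gives the out-of-season score a negative-control role. Exclusion criterion 4 removes people with moderate to severe rhinitis from regular exposures or treated tree-pollen rhinitis, so out-of-season scores may be low. The documents give no out-of-season values from which to judge this.

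**Conclusion.** The gap is real and minor. SAP 9.2.8 gives no treatment estimate with out-of-season MRSUI as the outcome in any year, S15 enters no model, and Section 13 is silent. SAP Section 3 cannot be dismissed as text carried over unedited: it adds peak TNSS and sneeze count, which the protocol lists do not contain, and keeps the out-of-season wording.

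A reader might infer that the in-season key secondary is compromised. It is not. Its estimate, its place in Table 2, the primary endpoint and all alpha-controlled tests are unchanged. SAP 8.5 already makes p-values outside Table 2 descriptive. The loss is a supportive result and some context for interpretation.

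This rests on S5, S10 and S15 being the out-of-season assessments, as Appendix 5 shows, and on the worked example in 9.2.8 fixing the direction of subtraction for all years.

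**What to change.** Add one supportive repeated-measures model to SAP 9.2.8: out-of-season MRSUI at S5, S10 and S15 as the outcome, the treatment, year and interaction terms and covariance of Section 9.1.2, and Visit 0 MRSUI as covariate. Report the combination versus double-placebo difference at year 3, and at years 1 and 2, with confidence intervals beside the in-season result and outside the multiplicity procedure.

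Record the departure from Protocol 13.3.4.1 in SAP Section 13 or the study report. The note at the end of the SAP was written after finalisation and database lock, so a model added after lock must be labelled post hoc. If no model is added, the minimum is to state that the MRSUI analysis was limited to the in-season outcome and that this differs from the protocol.

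The cost is one model, one table and one sentence of disclosure, using assessments already in the schedule. No alpha is spent and no existing analysis changes.

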9.3. Other Endpoints

All exploratory endpoints will be treated as supportive and will mostly focus on point estimates and 95% confidence intervals. P-values computed for analyses of exploratory endpoints will not be adjusted for multiplicity and are to be treated as descriptive only. Unless otherwise noted, all analyses will be performed on data from the mITT sample and will be analyzed using the same models as described above for the secondary endpoints.

9.3.1. Clinical Tolerance and Clinical Desensitization Endpoints

These exploratory endpoints mirror all secondary endpoints, but focused on the other pairwise treatment comparisons at years 1, 2, and 3 for:

- SLIT plus dupilumab placebo arm *versus* double-placebo arm*
- Combination of SLIT and dupilumab arm *versus* SLIT plus dupilumab placebo arm

*Note that as per [Section 9.2.1](#), the year 2 treatment difference for TNSS AUC_{0-1hr} for the treatment comparison of SLIT/dupilumab arm *versus* SLIT plus dupilumab placebo arm, is an exception given this comparison is a key secondary endpoint and therefore part of the multiplicity control. All other endpoints for these two above pairwise treatment comparisons are considered exploratory. See [Section 8.5](#) for details of which endpoints are part of the multiplicity control.

9.3.2. Total sneeze count (0-15 minutes) from NAC

The total number of sneezes from 0 to 15 minutes, as collected as part of the NAC, will be analyzed using a generalized Poisson linear mixed model (Stroup 2013, SAS Institute 2015). Often overdispersion occurs because of an incorrect variance function from count data. To adjust the count data models for the likely overdispersion, the data will be modeled using the generalized Poisson distribution, which introduces a scale parameter. The advantage of this distribution is that when no overdispersion is observed, the generalized Poisson reduces to a Poisson distribution.

The generalized Poisson linear mixed model will analyze the total sneeze count data from years 1, 2, and 3 and will include fixed effects for treatment arm (all 3 levels), time (i.e. year), and treatment arm by time interaction. Time will be treated as a categorical variable (with 3 levels = year 1, year 2, and year 3). The model will also include a random intercept to account for the longitudinal design. Note that the number of sneezes was not collected at the screening/baseline NAC so no adjustment for baseline sneeze count will be made.

Given the nature of modelling using a Poisson distribution, the LS means with associated 95% confidence intervals (CIs) for each treatment arm and time point (as well as LS means treatment differences for each pairwise comparison), will be obtained by exponentiating the model estimates.

9.3.3. Pulmonary Function Spirometry Tests

Descriptive statistics of spirometry results and change from baseline results will be summarized for each treatment group and overall. Data listings will also be provided.

9.4. Examination of Subgroups

All subgroup examinations will be exploratory in nature, with a purpose to explore the uniformity of any treatment effects found overall.

First, subgroup analyses of the primary endpoint will include repeating the primary analysis of the primary endpoint using a longitudinal repeated measures model adjusting for treatment arm, time, baseline TNSS AUC_{0-1hr}, and the baseline ratio of grass pollen specific-IgE to total IgE. An interaction term will also be included between the ratio of grass pollen specific-IgE to total IgE and treatment arm, to evaluate if the treatment effect on the primary endpoint is modified by differing levels of the ratio of grass pollen specific-IgE to total IgE. The interaction effect between the treatment group and the subgroup variable will be tested using a Type III fixed effects test.

The same modeling approach will be employed to evaluate if the treatment effect on the primary endpoint is modified by differing levels of:

- baseline grass pollen specific-IgE (i.e. the values alone, not as a ratio to total IgE)
- baseline grass pollen skin prick test wheal size (mm).

Second, subgroup analyses of the primary endpoint will repeat the primary analysis model for the primary endpoint using a *separate* model for each subgroup level. Repeat for the following subgroup levels:

- Age (years): $<$ median and \geq median
- Sex: male and female
- Race: white, black, Asian, mixed, and other (including unknown/not reported); race categories that have a low sample size may be combined

10. SAFETY EVALUATION

10.1. Overview of Safety Analysis Methods

All safety summaries will be created using the Safety sample, unless otherwise specified. Missing safety information will not be imputed.

Listings will be prepared for all safety measurements, as required for the clinical study report. All listings will be sorted in order of treatment, subject identifier (ID), and time of assessment (e.g., visit, date, and/or time).

10.2. Extent of Exposure

No other summaries for exposure will be created other than the treatment compliance summaries per [Section 7.3](#) above.

10.3. Adverse Events

Adverse events for this study are defined as per the protocol section 12.2.1.

For purposes of analysis, treatment-emergent adverse events (TEAEs) will be defined as all reported AEs with a start date on or after the first date of study treatment.

In order to assign treatment-emergence status, partial or completely missing AE start dates will be imputed using the algorithm in [Appendix 15.3](#).

All AEs will be classified by system organ class (SOC) and preferred term (PT), according to Medical Dictionary for Regulatory Activities (MedDRA), version 23.1 or later.

The severity of AEs will be classified using various grading criteria depending on the type of AE as follows:

Type of AE	Name of Severity Grade Criteria	Grading Scale
All local reactions to SLIT	Grading Table for Local Reactions to SLIT	Grade 1, 2, 3, or 4
All local reactions to allergen skin testing	Grading Table for Local Reactions to Allergen Skin Testing	Grade 1, 2, or 3
All local reactions to the NAC procedure	NAC procedure (local reactions)	Grade 1, 2, 3, or 4
Any immediate (0-1hr) systemic allergic reaction that occurred following administration of either SLIT or dupilumab All systemic reactions related to allergen skin testing or to the NAC procedure	WAO Subcutaneous Immunotherapy Systemic Reaction Grading System	Grade 1, 2, 3, 4, or 5 (where 5 = death)

DAIT NIAID Immune Tolerance Network
Statistical Analysis Plan - ITN084AD GRADUATE

All local reactions to dupilumab All other AEs	National Cancer Institute's (NCI's) Common Toxicity Criteria for Adverse Events (CTCAE) v5.0	Grade 1, 2, 3, 4, or 5 (where 5 = death)
---	--	---

Note: See protocol section 12.3.1 for the definitions of each grading criteria.

Each AE is entered on the case report form (CRF) once at the highest severity. As such, no additional data manipulation is needed to identify events.

AE summaries during screening (i.e., any time pre-treatment for treated participants, or during screening period for non-treated participants) will be performed using the Screened sample. All other AE summaries will be performed for only treatment-emergent events by treatment arm using the Safety sample.

An overall summary table will be created separately for 1.) during screening and 2.) only treatment-emergent events, to report the number of events and the number and percentage of participants having at least one event in the following categories. Categories with an asterisk (*) below are only relevant for the treatment-emergent summary (not during screening period).

- Any AE
- Any AE indicated as serious
- Any AE that led to study drug discontinuation*
- Any AE with an outcome of death
- Any AE that was reported as being related to any study drug*
 - Any AE that was reported as being related to SLIT
 - Any AE that was reported as being related to dupilumab
- Any AE that was reported as being related to any study procedure
 - Any AE that was reported as being related to skin prick test
 - Any AE that was reported as being related to NAC procedure
 - Any AE that was reported as being related to venipuncture
- AEs reported by maximum severity grade (all severity grade criteria combined)
- AEs reported by maximum severity grade (within each severity grade criteria separately)

For purposes of assigning relatedness to study drugs, “related” will be considered for analysis purposes if relationship entered on eCRF is “Possibly Related”, “Related”, or missing.

For purposes of assigning relatedness to study procedures, “related” will be considered for analysis purposes if relationship entered on eCRF is “Possibly Related” or “Related”. A missing category will be separately considered.

In addition, AEs classified by MedDRA SOC and PT will be summarized for each treatment group and overall, separately for 1.) during screening and 2.) only treatment-emergent events. These SOC/PT summaries will be repeated for each of the following categories:

- Any AE
- AEs by maximum severity (all severity grade criteria combined)
- AEs by maximum severity (within each severity grade criteria separately)
- SAEs by maximum severity (all severity grade criteria combined)
- SAEs by maximum severity (within each severity grade criteria separately)
- AEs by relationship to study drug (only applicable to treatment-emergent summary)
- AEs by relationship to study procedure (both screening and treatment-emergent summaries)

Summary tables will present the total number of events, as well as the number and percentage of participants experiencing the events. If a participant experiences the same AE on multiple occasions, the event will be counted for each occurrence when reporting the number of events. When reporting the number of participants experiencing the events, a participant will only be counted once if they experience an event within the particular SOC or PT. Percentages will be based on the number of participants in the analysis sample of interest.

In addition to the above treatment-emergent summaries at any time post-treatment, AEs will be summarized during year 1, 2, and 3 separately using the following displays:

- Overall summary (repeated with same categories as above)
- Any AE by SOC/PT
- AEs by maximum severity (all severity grade criteria combined)
- SAEs by maximum severity (all severity grade criteria combined)
- AEs by relationship to study drug

For the above AE year intervals, the analysis windows are as follows for counting events:

Year Interval	Lower Bound	Upper Bound
Year 1 (Week 0 through <Week 54)	Study Day 1 (first treatment date)*	Study Day 377
Year 2 (Week 54 through < Week 108)	Study Day 378	Study Day 755
Year 3 (Week 108 onwards)	Study Day 756	No upper bound

*Study day is defined per [Section 8](#) of this SAP.

The denominators for percentages will be for each time interval as follows:

Year Interval	Denominator Subset
Year 1 (Week 0 through <Week 54)	All participants in the Safety sample
Year 2 (Week 54 through < Week 108)	All participants in the Safety sample who remained in the study through Study Day 378
Year 3 (Week 108 onwards)	All participants in the Safety sample who remained in the study through Study Day 756

The study day for inclusion for denominators will be based on the maximum of 1.) end of study date, 2.) date of most-recent follow-up, and 3.) last AE start date.

